8.5. Variables

Adherence is defined as percentage of time with medication on hand and will be assessed with the Medication Possession Ratio (MPR) and Proportion of Days Covered (PDC). Both measures have been evaluated in numerous publications for rheumatoid arthritis and other conditions and will be reported in current study for 6 and 12-month follow-up periods. Both

adherence measures will leverage tofacitinib medication days supply in the numerator, for which PDC adjusts for overlap in prescriptions while MPR does not. Further, the PDC is a more conservative measure of adherence as the denominator includes all pre-defined follow-up (360 days for the 12-month period; 180 days for the 6-month period), which may include time after stopping a medication in the calculation, while MPR only includes time between first and last prescription (plus last prescription days supply) in the denominator. Patients with an MPR or PDC ≥ 0.8 are typically characterized as adherent. The Pharmacy Quality Alliance recommends use of PDCs for adherence measurements.⁸

The proportion of patients who are persistent with treatment is also commonly evaluated in similar published studies and will be reported for 6 and 12-month follow-up periods. Prior studies have indicated at least 1/3rd of patients are not persistent with TNFi therapy, which is consistent with proportion of patients with inadequate response in clinical trials.⁵ This measure takes into account patients who have not discontinued (gap of 60 days between refills) or switched medications; however, it may underestimate the proportion who are persistent depending on the duration of gap (ie, 60 vs. 90 days) for patients that may appear to discontinue and resume treatment for multiple reasons including hospitalization, drug samples not recorded in claims, use of stockpile, etc. Hence sensitivity analyses with different gaps are often employed.

Two measures of effectiveness will be used in this study: 1) a validated algorithm-based, dichotomous measure (over the 12 month follow up period) and 2) a duration of therapy based continuous measure of medication persistence (over 6 and 12 month follow up periods).

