Among patients with at least one year of follow up, medication effectiveness at one year after the index date will be determined using an algorithm-based proxy measure of effectiveness based on the following six criteria.^{3,7} This measure was shown to have good sensitivity, specificity, positive and negative predictive values ranging from 75% to 90% using a gold standard of low disease activity (DAS28 ≤ 3.2) or improvement in DAS28 by >1.2 units, which the authors suggested was consistent with but not identical to European League Against Rheumatoid Arthritis (EULAR) responder definition.³

The second effectiveness proxy is length of treatment duration which captures both the sustained positive treatment effect as well as inefficacy, loss of efficacy and adverse events as well as any discontinuations unrelated to treatment effect, such as costs and adherence.¹¹ Note that the MR and IR tofacitinib formulations have same costs. Duration of therapy has been used as an endpoint to demonstrate the improved effectiveness of methotrexate relative to other csDMARDs despite similar efficacy in RCT.¹¹ In this study, treatment duration was defined as the number of days between index date to the first of the following: the date of last prescription that is followed by a gap of 60 days without evidence of another advanced therapy prior to expiration of gap; the day before receipt of another advanced therapy; or the end of follow up period.

Table 2. Variables Used in Analyses

Variable	Role	Operational definition
Index date	Baseline Patient Characteristics	Month and year of the patient's treatment index date (see Section 8.2.1 , 8.2.2).
Age	Baseline Patient Characteristics	Patient age as of the index date.
Age group	Baseline Patient Characteristics	Age categorized into: 18–44, 45–64, and 65+.
Sex	Baseline Patient Characteristics	Male or female.
Geographic region	Baseline Patient Characteristics	Region in which the study patient is enrolled in a health plan will be categorized into five geographic regions: Northeast, North Central, South, West, and Unknown.
Insurance type	Baseline Patient Characteristics	Insurance type (commercial or Medicare) of index claim.
bDMARD use, 12 month pre-index, categorical	Baseline Clinical Characteristics	The count of unique bDMARDs with at least one prescription (Annex 2) received during the 12 month pre-index period. Will characterize use of 0, 1, 2 or more bDMARDs.

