Length of variable length pre-index period, categorical	Baseline characteristic	Continuous variable length duration categorized into <13, 13-18, 19-24, 25-30,31-36 and >36 months.
CCI [REDACTED]	[REDACTED]	[REDACTED]
[REDACTED]	[REDACTED]	[REDACTED]
[REDACTED]	[REDACTED]	[REDACTED]
CCI [REDACTED]	[REDACTED]	[REDACTED]
[REDACTED]	[REDACTED]	[REDACTED]
CCI [REDACTED]	[REDACTED]	[REDACTED]
[REDACTED]	[REDACTED]	[REDACTED]
[REDACTED]	[REDACTED]	[REDACTED]

Table 2. Variables Used in Analyses

Variable	Role	Operational definition
CCI [REDACTED]	[REDACTED]	[REDACTED]
Treatment Persistent, 6 and 12 months post-index, dichotomous	Outcome (persistence)	
Patients who do not have a switch to another advanced therapy or discontinue tofacitinib (ie, 60-day gap between the run out of prior tofacitinib prescription and subsequent fill) over 6 and 12 month follow-up periods are characterized as persistent. The run out date is the prescription fill date + day supply – 1. For retail outpatient pharmacy prescription (RX) claims, the day supply will be utilized. There are no null tofacitinib days supply in dataset; however, claims with negative days supply or zero days supply will be excluded. Most tofacitinib prescriptions are for 30 days supply (86%) followed by 90 (12%) and 60 (~1%) days.
 
Patients with early refills will be allowed to accumulate a stockpile of the index medication of up to 14 days for later use.
 
A change in the formulation of active ingredient prescribed, eg, 5 mg BID vs 11 mg QD is not considered a switch for persistence endpoints in primary analyses.

Medication Possession Ratio (MPR), 6 and 12 months post-index, continuous	Outcome (adherence)	
The total days supply between the first and including the last tofacitinib prescription divided by the time between the first through and including last index therapy prescription days supply. Multiple prescriptions for the same treatment with the same fill date will be treated as one prescription with longest days supply; and for all prescriptions days supply will be capped at end of follow-up. MPR will be capped at 1.0 and will be reported at 6 months and 12 months.

Medication Possession Ratio (MPR), 6 and 12 months post-index, dichotomous	Outcome (adherence)	
High adherence (MPR\geq0.8) vs. Low Adherence (MPR <0.8).

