Oral glucocorticoids criterion	Effectiveness criterion 5	The oral glucocorticoids criterion is met if a) For patients with no oral glucocorticoid prescriptions in the 6 months prior to index date, there is not more than 30 total days supply of oral glucocorticoids between 3-12 months post index; b) For patients with at least one claim for oral glucocorticoids during 6 months pre-index, oral glucocorticoid dose does not increase during months 6-12 post-index compared to the 6 months before the index date. Dose increase is defined as $\geq 20\%$ increase in prednisone equivalent dose (per above) for all glucocorticoid claims filled during the respective time periods. Note: Patients with more than one glucocorticoid injection during months 3-12 after index will be evaluated per the injection glucocorticoid criterion .
Injection glucocorticoid criterion	Effectiveness criterion 6	The injectable glucocorticoids criterion is met if patients have one or fewer glucocorticoid injections during months 3-12 after index date. Patients having one or more glucocorticoid injections on a single day are not considered to have failed the criterion.
Medication effectiveness, Duration of therapy (persistence), continuous, 12 month post-index	Outcome (effectiveness proxy)	The number of days between index date to the first of the following: the date of last prescription that is followed by a gap of 60 days without evidence of another advanced therapy prior to expiration of gap; the day before receipt of another advanced therapy; or the end of follow up period. A sensitivity analysis will be conducted for the Tofacitinib MR and IR comparison to include a switch in formulation as a criterion for discontinuation.

Table 3. Dose Escalation Criteria

Generic Name	Standard dosing schedule	Criteria for dose escalation for medication effectiveness
Tofacitinib (tofacitinib IR)	5 mg twice daily	At least 1 claim in the follow-up period with an average daily dose of at least 20 mg/day.
tofacitinib (tofacitinib MR)	11 mg once daily	At least 1 claim in the follow-up period with an average daily dose of at least 22 mg/day.

CCI

[REDACTED]

[REDACTED]

[REDACTED]

[REDACTED]

[REDACTED]

[REDACTED]

C
C
I

[REDACTED]

I

[REDACTED]

I

[REDACTED]

I

[REDACTED]

I

[REDACTED]

I

[REDACTED]

[REDACTED]

[REDACTED]

[REDACTED]

CCI

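### The primary duration-of-therapy rule dates a gap discontinuation at the last fill and leaves out that fill's supply, so a one-fill patient with no other advanced therapy before the gap expires scores 0 days

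*Combined protocol and SAP*

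**What the plan says.** The second effectiveness proxy is time on treatment. In the section 8.5 text "treatment duration was defined as the number of days between index date to the first of the following". Three end points follow. For a patient who stops without another advanced therapy before the gap expires, the end is "the date of last prescription that is followed by a gap of 60 days". The other two are "the day before receipt of another advanced therapy; or the end of follow up period". The duration row of Table 2 repeats the rule. Neither place adds days supply or says where the 60 days begin.

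Other measures in section 8.5 treat the last fill differently:

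- **Persistence (yes/no), Table 2.** The gap is a "60-day gap between the run out of prior tofacitinib prescription and subsequent fill". "The run out date is the prescription fill date + day supply", minus 1. Up to 14 days of stockpile may be carried forward.
- **MPR.** The text takes the time "between first and last prescription (plus last prescription days supply) in the denominator". Table 2 uses "the time between the first through and including last index therapy prescription days supply" and adds that "for all prescriptions days supply will be capped at end of follow-up".
- **PDC, Table 2.** Days covered by each fill are counted over 180 or 360 days, with the same 14-day stockpile.

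Section 8.2.1, criterion 1, requires the index fill to be a 30-day supply. Table 4 makes duration a primary endpoint at 12 months and a secondary one at 6 months, both by Cox regression. Section 8.9.2 promises means, medians and standard deviations for continuous measures, by cohort.

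**The concern.** Two things look wrong. First, the plan's measures disagree about one patient. With a single 30-day fill, no refill and no other advanced therapy before the gap expires, the MPR is 1.0, the PDC counts 30 covered days, and duration of therapy is 0. Second, the two kinds of event are dated on different bases. A switcher is credited up to the day before the new drug, including any uncovered days. A gap stopper is credited only to the last fill. A one-fill patient who switches on day 10 scores 9, while one whose supply ran to day 29 without a switch scores 0.

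At stake are the reported days on therapy for a primary endpoint and the internal consistency of the persistence and adherence results. The plan also gives no rule for an event at time 0 in the Cox model. The one sensitivity analysis attached to duration concerns formulation switching and does not touch this.

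**Working it through.** The plan states no expected duration or event rate, so there is no figure of its own to reproduce.

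**Step 1: one patient, from the definitions.** Index date is day 0; one 30-day fill (section 8.2.1).

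- Run-out = 0 + 30 - 1 = day 29.
- Gap counted from run-out expires at 29 + 60 = day 89.
- Gap stop, as written: 0 days. With run-out dating: 29 days.
- Switch on day 30: 30 - 1 = 29 days. Switch on day 89: 89 - 1 = 88 days.
- Switch after the gap expires: 0 days, because the gap end point comes first.
- MPR = 30/30 = 1.0. PDC at 12 months = 30/360 = 0.083.

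The 29-to-88 range depends on the gap starting at run-out. If it started at the fill date it would expire at about day 60, and a later switcher would also score 0. A fill-to-fill reading would also make any 90-day fill refilled on time look like a gap, since 90 exceeds 60. The start therefore needs stating.

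**Step 2: difference per gap stopper.** Run-out minus last fill = supply - 1, which is 29, 59 or 89 days for a 30-, 60- or 90-day last fill. Carried stockpile can add up to 14 (29 + 14 = 43 on a 30-day fill). Table 2 gives 86% of prescriptions at 30 days, 12% at 90 and about 1% at 60. If last fills follow that mix (an assumption, since it describes all prescriptions), the mean difference is (0.86 × 29 + 0.12 × 89 + 0.01 × 59) / 0.99 = 36.6 days.

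**Step 3: whole cohort, simulated.** Assumed inputs: constant hazard, back-to-back 30-day fills, 45% of enders switching, gap complete by day 360, and 12-month persistence of 40% to 67%. The top of that range matches the section 8.5 remark that at least a third of TNFi patients are not persistent. The shift in the cohort mean is 29 × the share of the cohort that are gap stops.

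| Persistence | Gap stops, share of cohort | Gap-stopper mean, last fill vs run-out (days) | Cohort mean lower by (days) | Gap stops at 0 days | Cohort at 0 days |
|---|---|---|---|---|---|
| 40% | 29.3% | 117 vs 146 | 29 × 0.293 = 8.5 | 13.7% | 4.0% |
| 50% | 24.1% | 121 vs 150 | 29 × 0.241 = 7.0 | 12.8% | 3.1% |
| 60% | 19.1% | 124 vs 153 | 29 × 0.191 = 5.5 | 12.1% | 2.3% |
| 67% | 15.6% | 127 vs 156 | 29 × 0.156 = 4.5 | 11.6% | 1.8% |

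If 12% of fills are 90-day, the cohort shift reaches about 13 days at 40% persistence.

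**Step 4: between arms.** The rule is the same in both arms, so a shift needs the arms to differ in how patients end. Simulated over 40-60% persistence with 30-day fills:

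- Switch share 40% vs 30%: the difference in means moves by 1.0 to 1.6 days and the hazard ratio by 0.2-0.7% (0.996 vs 1.000 at 50% persistence).
- Switch share 60% vs 30%, an extreme case: 3.0 to 4.7 days and 0.6-1.9%.
- With 12% of fills at 90 days, the largest shifts are 2.5 days and 1.0% (10 points), and 7.2 days and 2.9% (30 points).
- Equal switch shares, true hazard ratio 0.80, 50% persistence: hazard ratio 0.800 under both rules; difference in means 16.1 vs 15.0 days.

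**The case against.** The strongest reply is that run-out is not the true stopping date either. Claims record fills, not tablets taken. Section 8.5 says this proxy captures inefficacy and adverse events, and a patient who stops for such a reason may do so mid-supply. Last fill is then a lower bound and run-out an upper bound. If true stopping were uniform over a 30-day last fill, last-fill dating would be 14.5 days short on average and run-out dating 14.5 days long (29/2 each). This stands. A reader might infer that every gap stopper's duration is too short by the whole last fill; the documents do not support that.

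Second, the objectives are comparative and the planned analysis is Cox regression, where the choice barely matters. This also stands.

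Third, a reader might infer that the persistence and MPR rows contradict the duration row. Strictly they do not. The persistence row uses run-out to decide whether a gap exists and sets no end date for duration, and MPR is a ratio of supply to time. What remains is an inconsistency of treatment. Where the authors mean supply to count they say so, and here they do not.

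Fourth, footnote c to Table 4 is attached to the 12-month duration endpoint and is blacked out. It may state the end date or the gap start, so certainty is limited.

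**Conclusion.** The point holds as a definitional weakness in a primary endpoint that is worth fixing. Nothing visible in the protocol repairs it. Read as written, a patient dispensed 30 days of drug can score 0 days of therapy while counting as fully adherent on MPR. Relative to run-out dating, gap stoppers score 29, 59 or 89 days less, the cohort mean is about 4.5 to 8.5 days lower with 30-day fills, and about 2-4% of patients score 0. The cohort figures rest on assumed persistence, switching share, hazard shape and fill pattern; only the per-patient figures follow from the plan.

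These are differences between two conventions. A reader might also infer that the MR versus IR comparison is biased. The calculations do not support that: the rule is common to both arms, and the hazard ratio moves by at most 1.0% with a 10-point difference in switch share and 2.9% in the extreme case tried. The effect is on reported durations and internal consistency, not on the main comparison.

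**What to change.** Unless footnote c to Table 4 already does so:

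1. In the section 8.5 definition of treatment duration and the duration row of Table 2, end a gap discontinuation at the run-out date of the last fill as the persistence row defines it, with the 14-day stockpile and capped at the end of follow-up. Leave the switcher end date as planned.
2. Count the 60-day gap from run-out in both places, and in the section 8.5 paragraph on persistence, which now speaks only of refills.
3. Report last-fill dating as a sensitivity analysis. The two versions then bracket the possible stopping dates.
4. State that a gap still incomplete at the end of follow-up is censored, and how any event at time 0 enters the Cox model.

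The cost is wording in three places and a small programming change, with no new data. The downsides: gap stoppers' durations rise by about a month, become an upper bound on actual use, and are less comparable with studies that date stopping at the last fill. The gap between stoppers and switchers narrows but remains. A one-fill stopper would score 29, against 29 to 88 for a one-fill patient who switches after run-out and before the gap expires.

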8.2.2. Exclusion Criteria

Patients meeting any of the following criteria will not be included in any study cohort:

1. Patients with claims for other conditions for which advanced therapies (bDMARD or Janus Kinase inhibitor (JAK)) are used during the one-year pre-index period or on the index date: ankylosing spondylitis, Crohn's disease, psoriasis, psoriatic arthritis, juvenile idiopathic arthritis or ulcerative colitis will be excluded from the study.

Table 1. Exclusionary Diagnosis

Disease	ICD-9 diagnosis code	ICD10 diagnosis code
Ankylosing Spondylitis	720.0x	M45.*
Crohn's Disease	555.xx	K50.*
Psoriasis	696.1x	L40.0*-L40.4*, L40.8*- L40.9*
Psoriatic Arthritis	696.0x	L40.5*
Ulcerative Colitis	556.xx	K51.*
Juvenile RA	714.3*	M08.*

ICD: International classification of diseases; RA = rheumatoid arthritis

2. Patients with evidence of the index medication during the one-year pre-index period. Patients will be allowed to have been treated with other advanced therapies defined as other bDMARDs or other JAK inhibitors (not tofacitinib) during the one-year pre-index period.
3. Patients with more than one advanced therapy prescription fill on the index date will be removed from the study, ie, a bDMARD and JAK inhibitor or more than one JAK inhibitor or two different tofacitinib formulations (ie, IR and MR), filled on the index date will be removed from the study.

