Proportion of Days Covered (PDC), 6 and 12 months post-index, continuous	Outcome (adherence)	
The PDC was defined as number of days covered by arrays for each fill or administration during the denominator periods of 180 and 360 days post-index. Patients with early refills will be allowed to stockpile medications up to a maximum of 14 days total for later use. PDC is capped at 1.0.

Proportion of Days Covered (PDC), 6 and 12 months post-index, dichotomous	Outcome (adherence)	
High adherence (PDC\geq0.8) vs. Low Adherence (PDC <0.8).

Table 2. Variables Used in Analyses

Variable	Role	Operational definition
Medication Effectiveness, algorithm defined, 12 months post-index, dichotomous	Outcome (effectiveness)	Patients who meet all 6 effectiveness criteria will be considered effectively treated. Patients who fail any one of the 6 criteria are considered not effectively treated.
High adherence criterion	Effectiveness criterion 1	High adherence criterion met if PDC ≥ 0.8 during the 12 month follow-up period.
Dose escalation criterion	Effectiveness criterion 2	No dose escalation criterion is met if no increases in index medication dose between index and 12 months after index. Dose increase threshold defined per Table 3 .
No treatment switch criterion	Effectiveness criterion 3	No treatment switch criterion is met if there is no use of an advanced therapy (Annex 2) other than index therapy during the 12 month follow-up period.
Addition of csDMARD criterion	Effectiveness criterion 4	No addition of csDMARD criterion is met if there are no claims for any csDMARD during the 1-year post-index for which there was not a claim during 1-year pre-index and/or 90 days post-index.

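### A single later claim for another advanced therapy ends treatment duration and fails criterion 3 even when tofacitinib fills continue, and the readable plan has no check for carry-over fills of the previous drug

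*Combined protocol and SAP*

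**What the plan says.** **Who enters.** Section 8.2.2 permits earlier treatment in the pre-index year: "Patients will be allowed to have been treated with other advanced therapies defined as other bDMARDs or other JAK inhibitors". No washout is stated. The only protection against overlap concerns a single day: "Patients with more than one advanced therapy prescription fill on the index date will be removed from the study".

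**Duration of therapy (primary, 12 months).** Section 8.5, in the text and again in Table 2, ends duration at the first of three dates: the last prescription before a 60-day gap, "the day before receipt of another advanced therapy; or the end of follow up period".

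**Algorithm-defined effectiveness (primary, 12 months).** Table 2 meets criterion 3 only if "there is no use of an advanced therapy (Annex 2) other than index therapy during the 12 month follow-up period". The algorithm is all-or-nothing: "Patients who fail any one of the 6 criteria are considered not effectively treated".

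**Treatment Persistent.** Table 2 defines persistent patients as "Patients who do not have a switch to another advanced therapy or discontinue tofacitinib". The readable text does not say whether a switch requires tofacitinib to stop.

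**Sensitivity analysis.** The one attached to the duration outcome treats a change of tofacitinib formulation as discontinuation. It does not deal with overlapping fills of other advanced therapies.

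**The concern.** The cohort may include patients moving directly from a biologic or another JAK inhibitor. A last shipment of the old drug can plausibly be dated a few days after the first tofacitinib fill. On day 0 that claim removes the patient. On day 1 or later it keeps the patient in and, under the readable rules, cuts duration to a few days and fails criterion 3, however long tofacitinib is then taken. A move onto tofacitinib is scored like a move off it.

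The plan makes allowance for carry-over in other places. Criterion 4 ignores conventional synthetic DMARDs already claimed in the pre-index year or first claimed within 90 days after index. The injection criterion, and the oral glucocorticoid criterion for patients without recent use, start counting at month 3; for patients with recent oral use the comparison starts at month 6. Criterion 3 and the duration rule have no similar allowance.

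Both primary effectiveness proxies are exposed, and Treatment Persistent is too if such a claim is read as a switch. The same patient can then be fully adherent on the primary adherence endpoints and an almost immediate failure on the primary effectiveness endpoints.

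**Working it through.** The plan states no frequency, power or effect size for this point, so there is no figure to reproduce. The check applies the written rules to one claims history and then shows a range under stated assumptions.

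**1. One patient under the written rules**

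Inputs: 360-day follow-up (section 8.5, the PDC denominator); 12 tofacitinib fills of 30 days with no gaps; one fill of another advanced therapy on day *k* after index.

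- PDC = 12 × 30 / 360 = 1.00, so criterion 1 (at least 0.8) is met. MPR = 360 / 360 = 1.00.
- Duration = min(360, *k* − 1), since no 60-day gap occurs.
- Criterion 3 is met only if there is no other advanced therapy.

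| Other-therapy fill | Duration (days) | Criterion 3 | Algorithm result |
|---|---|---|---|
| none | 360 | met | depends on the other criteria |
| day 3 | 2 | failed | not effective |
| day 5 | 4 | failed | not effective |
| day 14 | 13 | failed | not effective |
| day 30 | 29 | failed | not effective |

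If the stray claim did not count as a switch when tofacitinib is refilled afterwards, each of these rows would return to 360 days with criterion 3 met.

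**2. Effect on levels (assumed shares)**

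Let *q* be the share of otherwise fully persistent patients with a stray fill on day 7. The loss in mean duration in that group is *q* × (360 − 6). An assumed effective share of 30% becomes 0.30 × (1 − *q*).

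- *q* = 1%: 3.5 days; 29.7%
- *q* = 5%: 17.7 days; 28.5%
- *q* = 10%: 35.4 days; 27.0%

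If 60% of the cohort is advanced-therapy-experienced and 2% to 10% of those have a carry-over fill, the affected share of the cohort is 0.6 × 0.02 = 1.2% to 0.6 × 0.10 = 6%. With true 12-month persistence of 50%, measured persistence falls by 0.5 × 1.2% = 0.6 to 0.5 × 6% = 3 points, provided the claim is read as a switch.

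**3. Effect on the MR-IR hazard ratio (assumed; early end taken as an event)**

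Assume 50% persistence at day 360 in both cohorts and no true difference. The ratio of cumulative hazards is ln[0.5(1 − *q*₂)] / ln[0.5(1 − *q*₁)].

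- 2% against 5% of the whole cohort: ln(0.475) / ln(0.490) = 0.7444 / 0.7133 = 1.04.
- 2% against 5% of experienced patients, which is 1.2% against 3% of the cohort: ln(0.485) / ln(0.494) = 0.7236 / 0.7052 = 1.03.

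A simulated Cox model (exponential stopping, carry-over dates uniform over days 1 to 29, 200,000 patients per cohort) gives about 1.06 for the first case and 1.03 to 1.04 for the second. With equal carry-over in both cohorts, no true difference stays at 1.00, and a true hazard ratio of 0.85 moves to between 0.85 and 0.87 for shares of 1.2% to 6%.

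**The case against.** **A new advanced therapy after index is a reasonable failure marker.** Section 8.5 presents duration as an effectiveness proxy that captures inefficacy and adverse events, and criterion 3 belongs to an algorithm described as validated. This stands as a reason to keep criterion 3 in the primary analysis. It does not explain why a leftover fill of the previous drug, followed by a year of tofacitinib, should signal failure. Section 8.11 itself notes that tofacitinib was approved for RA after the algorithm was developed and that modifications may be needed.

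**Partial safeguards exist.** Number of prior advanced therapies is a fixed covariate (section 8.9.3), and Table 4 footnote b reports failures on each of the six criteria. Both help. Neither corrects an individual misclassification or shows when the criterion 3 claim occurred.

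**Stratification.** A reader might infer that false failures distort a comparison across patients with 0, 1 and 2+ prior therapies. The documents do not support that. Footnote a repeats the MR-IR analyses by stratum, if feasible. A carry-over fill needs a prior therapy, so the 0-prior stratum is largely free of the problem and serves as a useful check.

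**Redaction.** The 12-month duration endpoint in Table 4 carries footnote c, which is blacked out, as are section 8.6 and parts of Table 2; the Annex 2 code lists are kept in the study folder. A switch rule there cannot be ruled out. The visible definitions point to none.

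**Event coding.** A reader might take the day-4 end as a Cox event by rule. The readable plan does not say which endings are events and which are censored. An event is the natural reading for a persistence measure, but it is an inference. Failure on criterion 3 is explicit.

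**Cause of imbalance.** Nothing in the documents shows that carry-over differs between MR and IR users, who take the same active substance at the same stated cost. Bias is therefore a possibility, not a finding.

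**Conclusion.** The point holds for the readable text. One claim for another advanced therapy dated after index ends duration and fails criterion 3, whether or not tofacitinib continues. Supply dispensed before index is not a later receipt and does not trigger the duration rule.

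For an affected patient the effect is large: 4 days instead of 360 in the example, and not effectively treated whatever the other five criteria show. For the study it is probably modest, and its size cannot be derived from the documents, because the carry-over rate, the experienced share, the persistence level and any MR-IR imbalance are all assumptions. Equal carry-over slightly dilutes the contrast. The assumed imbalances examined move a null hazard ratio to about 1.03 to 1.06, conditional on the early end being an event. Only advanced-therapy-experienced patients are affected.

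A reader might go further and conclude that the MR-IR result is known to be biased, or that the primary criterion 3 must be replaced. The documents support neither. They do support measuring the frequency and testing whether the result depends on it.

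**What to change.** 1. Keep criterion 3 as written in the primary analysis, so that the algorithm stays comparable with its published form, and leave the primary duration rule unchanged.
2. Report, by cohort, the number of patients with a claim within 30 days after index for an advanced therapy already claimed in the 12 months pre-index and followed by a further tofacitinib fill.
3. Pre-specify a sensitivity analysis of both 12-month effectiveness endpoints, and of Treatment Persistent, in which those claims do not count as a switch. All other switches stay as defined.
4. State which endings of treatment duration are Cox events and which are censored, and whether a switch under Treatment Persistent requires tofacitinib to stop, unless redacted text already does so.

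The cost is a few lines of definition and programming on claims already extracted. The 30-day window is a working choice and should be labelled as one. The downside is that a few true early returns to the previous drug that still show one later tofacitinib fill would be dated later. That error is confined to the sensitivity analysis, and the primary result beside it shows how much it matters.
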